## 7.6. Storage

The IP must be transported and stored at a temperature not exceeding 30°C. It is recommended to store IP at room temperature. The IP should not be used beyond the expiry date indicated on the label.

The storage conditions, including the temperature, at the study centres must be monitored by the study personnel and appropriate records must be available. Any temperature excursion should be recorded and reported to DND*i*.

### 7.7. Blinding and procedures for unblinding

#### 7.7.1. Blinding Measures

Investigators, personnel of the clinical sites, the Sponsor (including biostatistics and data management personnel and the study monitors), and the participants will remain blinded during the study (i.e. until database lock). To ensure the double blind conditions of the study, acoziborole and matching placebo tablets will be identical in appearance. The packaging and labelling will be designed to maintain blinding of the Sponsor, study personnel and the subjects. The study data will remain blinded until the study database lock, and authorisation of data release according to standard operating procedures.

The randomisation list will be generated by Creapharm (packaging and labelling service providers) by respecting the ratio 3:1 using blocks of 16 kits.

The randomisation list is kept at Creapharm, who was in charge of assigning the kit number for the replacement of the 8 first subjects lost to follow-up.

Randomization data will be kept strictly confidential until the time of final database lock and will not be accessible by anyone else involved in the study, with the following exceptions:

- SGS, the bioanalyst for PK analysis (to avoid the unnecessary analysis of placebo samples)
- The independent statistician from PhinC, who will be in charge of analysing the correlation between ECG measurements and acoziborole concentrations at Day 5
- The designated person from DNDi Pharmacovigilance (or delegate), who will be in charge of unblinding of suspected unexpected serious adverse reaction (SUSARs) in case of exceptional request from the Health Authorities for regulatory safety reporting.
- The designated DNDi unblinded statistician, who will receive a scratching list to be used for individual unblinding in case of request from DSMB members

To ensure maintenance of the blinding during the study, a specific analytical code for PK and ECG analysis will be generated.

#### 7.7.2. Unblinding Measures

If unblinding is required in the interest of the safety of a subject, the site Investigator will discuss the matter with the Sponsor/Study Principal Investigator and/or the National Coordinating Investigator before scratching the individual code-break card for that subject, unless in a medical emergency, when the site Investigator or delegate may open the individual code-break card for that subject without prior consultation with the Sponsor/Study Principal Investigator and/or the National Coordinating Investigator. The site Investigator or delegate will notify the Sponsor as soon as possible, i.e. within 24 hours if possible, that the randomisation code has been broken for the subject with the justification and the participant number.

If the randomisation code is broken by the Investigator, the reason will be fully documented in the appropriate document provided with the individual code-break card.

The DSMB may exceptionally request unblinding of certain subject(s) (e.g. in case of a major safety concern), but only if absolutely necessary, and always in accordance with the DSMB Charter, therefore preventing unblinding the sponsor personnel.

Treatment allocation of all trial participants will be unblinded after the database lock.

#### 7.8. Concomitant treatments

#### 7.8.1. Concomitant medication

If the subject requires treatment after administration of the IP, the Investigator should be informed and approve the proposed medication. Any medication used after inclusion in the study (defined as the date of the ICF signature) and/or during the follow-up period must be recorded in the case report form (CRF) specifying the reason for use.

Any medication used to treat an AE or a SAE must be recorded in the CRF and on the SAE reporting form.

Any essential medicine required during the study participation will be provided to the subject free of charge. The WHO List of Essential Medicines will be used as a reference guide for the treatment of any concomitant condition. For any chronic condition, the study team will take all necessary measures to ensure that the subject is referred to the most appropriate healthcare facility in the region.

#### 7.8.2. Contraception

Preclinical studies showed that acoziborole has no effect on fertility or on post-natal development. However, as a precautionary measure in the absence of sufficient human pregnancy data, women of reproductive age will be advised to have protected sexual relations during the screening period and up to 3 months after receiving the study drug. Contraceptive methods will be made available to subjects free of charge throughout the duration of their participation in the study.

#### 7.9. Medical cares after trial ended

At the end of the study, after unblinding, the NSSCP will be informed of the subjects' study status (TL results at baseline, treatment arm and parasitology results at EoS) for appropriate follow-up according to NSSCP policy as follows:

- a) those included in the study and treated with acoziborole and TL positive
- b) those included in the study and treated with acoziborole and TL negative
- c) those included in the study treated with placebo and TL positive
- d) those included in the study treated with placebo and TL negative.

Since the inclusion time-period is expected to last for 12 months and the follow-up is planned for 4 months after treatment, the first study subjects included in the study may have to wait 1 year before knowing whether he/she has been treated with acoziborole or placebo. Therefore, while waiting for the end of the study, and the unblinding, subjects who conclude their 4 months of follow-up study visit (and especially those with TL positive results) will be referred to the NSSCP for the continuation of the NSSCP's standard follow-up management.

For follow-up of women who become pregnant during the study and their newborn babies after the end of their trial participation, please refer to Section 8.5.9.

#### 8. Study Assessments

Eligible subjects will be enrolled after they provide informed consent(s). Subjects will be hospitalised at least 1 day before study treatment commences and will be randomised in a 3:1 ratio to acoziborole or matched placebo arms on Day 1 of the study. Following hospitalisation, subjects will attend visits at the study centre at 1- and 4-months post-treatment and investigator contact between the site and study subjects will be established at 2- and 3-months post-treatment to encourage study adherence and ensure close follow-up of subjects. If deemed necessary by the investigator, an on-site unscheduled visit will be proposed to the subject. Any subject with a positive parasitological test result during the study will end their participation in the study and be referred to the NSSCP for appropriate standardised treatment.

Any premature discontinuation of a subject will be recorded with the reason in the CRF.

#### 8.1. Timing of assessments

The timing of all required assessments is presented in the schedule of activities (Section 5, Table 1).

- Days -2 to D1H0 (before dosing): signature of the ICF (main study and possibly TrypSkin sub-study) and baseline assessments
- Day 1 H0: randomisation and administration of acoziborole or matching placebo tablets
- Days 1 to 5: observation period at hospital
- Day 5: end-of-hospitalisation visit
- Out-patient follow-up visits at 1 months and 4 months (see Table 2). The timing of follow-up visits is calculated from Day 1
- Investigator contacts at 2 and 3 months to ensure close follow-up of subjects and encourage study adherence. An on-site unscheduled visit will be proposed if deemed necessary by the investigator.

#### Table 2. Theoretical schedule of visits and acceptable time window

Theoretical schedule of visits	Ideal timing of visits	Acceptable time window 			
End-of-hospitalisation visit	Day 5	Day 5 + 3 days			
1 month	1 month (Day 31)	1 month (Day 31) ± 10 days (i.e. between Days 21 and 41)			
4 months	4 months (Day 121)	4 months (Day 121) -10 days; +1 month (i.e. between Days 111 and 151)			

 The acceptable time window for the visit starts on the first day of the period mentioned and ends on the last day of the period mentioned.

#### 8.1.1. Baseline assessments (Day -2 to Day 1 before dosing)

The following assessments will be conducted to confirm subjects' g-HAT seropositive status and to check conformance with inclusion and exclusion criteria:

- Collection of informed consent(s)
- Collection of demographic data
- Review of inclusion/exclusion criteria
- Recording of concomitant medications
- Recording of medical history
- Serological test (HAT Sero-K-Set RDT or CATT) to confirm g-HAT seropositive status.
- Collection of blood/lymph for parasitological testing (m-AECT or mAECT-BC and lymph node aspirate if lymphadenopathy is present).
- Urine pregnancy test (women of childbearing potential only).
- Collection of dried blood spots for TL analysis.
- Collection of blood samples for assessment of haematology and biochemistry parameters
- Physical and clinical examination (including assessment of eventual signs and symptoms that might suggest HAT disease, vital signs, body weight and height)
- Dermatological examination
- Blood pressure (will be taken 1 hour (± 1 hour) prior the administration of the study drug)

- Karnofsky index
- Triplicate ECG at 2 minutes intervals will be recorded according to acceptable time window described in section 8.3.6)
- Collection of AEs

For subjects participating in the TrypSkin sub-study, the following assessment will be performed:

- Sampling of 3 mL fresh blood (in preservative buffer) and 250 µL in 5 DBS
- Sampling of two 2 mm-skin-punch biopsies on the right back shoulder under local anaesthesia

## 8.1.2. Assessments post study drug administration

## 8.1.2.1. Assessments during observation period at the hospital

The following procedures will be performed every day throughout the hospitalisation period:

- Collection of concomitant medications
- Collection of AEs

## Assessment at Day 1

• Blood pressure will be taken 4 hours (± 1 hour) and 9 hours (± 1 hour) after the study drug administration.

## Assessment at Day 5 (End of Hospitalisation Day):

- Physical and clinical examination (including assessment of eventual signs and symptoms that might suggest HAT disease, vital signs, body weight and height)
- Blood sampling for assessment of haematology and biochemistry parameters, and PK
- Recording of triplicate ECG at 2 minutes intervals

#### 8.1.2.2. Follow-up period assessments

All efforts should be made to follow-up the subjects for 4 months.

#### Assessments at the 1-month follow-up visit:

- Urine pregnancy test (women of childbearing potential only)
- Collection of blood/lymph for parasitological testing
- Physical and clinical examination (including assessment of eventual signs and symptoms that might suggest HAT disease, vital signs, body weight and height)
- Dermatological examination
- Karnofsky index
- Recording of concomitant medications
- Collection of AEs
- Blood sampling for assessment of haematology and biochemistry parameters, and PK

#### Assessments on 4-month follow-up visit (end of study visit):

- Recording of concomitant medications
- Collection of AEs
- Serological test (CATT or HAT Sero-K-Set RDT, same test than the one used at baseline to be repeated)
- Collection of blood/lymph for parasitological testing
- Urine pregnancy test (women of childbearing potential only)

- Physical and clinical examination (including assessment of eventual signs and symptoms that might suggest HAT disease, vital signs, body weight and height)
- Karnofsky index
- Dermatological examination
- Blood sampling for assessment of haematology and biochemistry parameters

For subjects participating in the TrypSkin sub-study, the following assessment will be performed:

- Sampling of 3 mL fresh blood (in preservative buffer) and 5 DBS
- Sampling of two 2 mm-skin-punch biopsies on the right back shoulder under local anaesthesia

#### 8.2. Assessment of efficacy

This study is not designed to evaluate efficacy.

#### 8.3. Assessment of safety

Full details regarding the laboratory procedures described in this section will be described in the laboratory manual.

#### 8.3.1. Laboratory examinations

Blood samples will be taken for assessment of haematology and biochemistry parameters during the screening period, on Day 5 of the hospitalisation period, Month 1 of the follow-up period, and at the EoS visit at Month 4.

The following laboratory parameters will be assessed:

- Haematology:
  - Haemoglobin
  - WBC count (and formula if WBC value is found abnormal)
  - platelet count
- Biochemistry:
  - Alanine Aminotransferase
  - o Albumin
  - Alkaline Phosphatase
  - Aspartate Aminotransferase
  - o **Calcium**
  - o Chloride
  - Creatinine
  - o Glucose
  - o Potassium
  - o Sodium
  - Total Bilirubin
  - Total Carbon Dioxide
  - Total Protein
  - Blood Urea Nitrogen

Clinically significant abnormalities in laboratory safety parameters must be recorded as AEs or medical history if recorded at baseline (see section 8.5.2).

#### 8.3.2. Parasitology assessments

Assessments for presence of parasites using mAECT or mAECT-BC will be conducted during screening period, at Month 1, and at the EoS visit at Month 4. The most sensitive parasitological test (m-AECT-BC technique [16]) will be preferred to detect the presence of trypanosomes in blood. When indicated, lymph node aspirate will also be used to

microscopically detect the presence of trypanosomes.

### 8.3.3. Trypanolysis tests

Two Whatman n°4 filter papers containing eight dried blood spots of 70  $\mu$ L each will be collected for each subject at screening to assess the presence or absence of antibodies against *T.b. gambiense*.

The TL test is only performed in a reference laboratory and receipt of test results can be delayed for several weeks. Therefore, TL results will not be a criterion for inclusion, but to classify subjects at the end of the study for addition in the final data analysis and to ensure proper follow-up of subjects. If TL is positive, there is a higher probability of the subject being a true case. Upon exiting the study and as soon as TL results are available, TL positive individuals will be referred to the NSSCP by the clinical site for appropriate surveillance. Upon study unblinding, the treatment received by the study participants will be communicated to the NSSCP to ensure that the TL positive individuals having received placebo have the parasitology follow-up assessments conducted. Those who are lost to follow-up will be reported to NSSCP.

#### 8.3.4. Pharmacokinetic analyses

PK analyses will be performed at Day 5 (steady state) and Month 1 (in accordance with acceptable time window of Table 3).

Whole blood (5 x 10  $\mu$ L) will be deposited on filter paper using the DBS technique and shipped to the reference laboratory for analyses.

For the first 192 subjects administered with the study drug, and who have a valid ECG and a PK sample at D5, PK samples will be analysed to assess correlation between  $\Delta QTc$  measurements (ECG assessment) and acoziborole DBS concentrations at D5.

The rest of PK samples will be stored and could be analysed in case of unexpected AE, if the samples are still within the stability deadline.

#### Table 3. Schedule of PK sample collection

Ideal timing of PK sample collection	Acceptable time window				
Day 5: 96 hours after intake of IP	± 1 hour				
Month 1: 30 days after intake of IP	± 10 days (between Days 21 and 41)				

IP=investigational product; PK=pharmacokinetic.

#### 8.3.5. Clinical and physical examination

Subjects will undergo clinical and physical examination including assessment of eventual signs and symptoms that might suggest HAT disease and vital signs at screening and Day 5 during the hospitalisation period, at the follow-up visit at Month 1, and at the EoS visit at Month 4.

Blood pressure of subjects will also be taken at screening, at D1 (1 hour before dosing, at H4 and at H9), at D5, at the follow-up visit at Month 1, and at the EoS visit at Month 4.

#### 8.3.6. Electrocardiogram

ECG measurements will be made in triplicate prior to administration of the study drug (Day 1) and at Day 5 in accordance with acceptable time window described in Table 4. The tracings will be recorded after a 20-minute rest interval and before collection of the blood samples for the PK analyses.

#### Table 4. Schedule of ECG recordings

Ideal timing of ECG recordings	Acceptable time window
(after 20-minute rest interval and before PK sampling)	Acceptable time window

Day 1: before intake of IP	within 1.5 hour before intake of IP
Day 5: 96 hours after intake of IP	± 1 hour

ECG=electrocardiogram; IP=investigational product; PK=pharmacokinetic.

Electrocardiogram for all subjects will be collected but only data from the first 192 subjects administered with the study drug and who have a valid ECG and a PK sample at D5, will be analysed to assess effect of acoziborole versus placebo at D5. If any signal is detected in this first analysis, all ECG collected will be then analysed. If no signal is detected, ECGs collected for other subjects will be used for safety documentation purposes.

## 8.3.7. Pregnancy test

Females of childbearing potential will undergo a urine pregnancy test at screening, at followup visit on Months 1, and at the EoS visit at Month 4.

## 8.3.8. Other assessments

The blood leftover from PK sampling at D5 will be kept and stored until the end of the study to be potentially used for genotyping in case of unexpected AEs. These samples will be destroyed at the end of the study (defined as the release of the Clinical Study Report).

## 8.4. Exploratory assessments

For subjects participating in the TrypSkin exploratory sub-study, the following samples will be taken at screening (baseline) and 4 months (EoS):

- 3 mL fresh blood (in nucleic acid-preservative buffer) and 5 DBS
- Two 2 mm-skin-punch biopsies on the right back shoulder under local anaesthesia

Samples will be shipped to specialised partner laboratories (Institut National de Recherche Biomédicale [INRB], Institut Pasteur Guinea and Institut Pasteur Paris and Institute of Tropical Medicine [ITM] Antwerp) for the following analyses:

1- Molecular detection of trypanosomes:

- Common automatised extraction of total nucleic acids (TNAs) from fresh blood, DBS and skin biopsies
- On TNAs from fresh blood and skin (main validated diagnostic methods):
  - For all samples: TBR-PCR and 18S-PCR (*T. brucei s.l.*)
  - For TBR-PCR+ and/or 18S-PCR+ samples: T.b. gambiense-specific TgSGP-PCR
- On TNAs from fresh blood, DBS and skin (additional methods to be tested):
  - o qPCR detection using at least 2 targets
  - Multiplex RT-qPCR detection using novel targets
  - CRISPR-derived approach (SHERLOCK)
- 2- Immuno-histochemical detection of dermal trypanosomes:
  - At least 2 automatised IHC on Formalin-Fixed Paraffin-Embedded (FFPE) skin sections for all subjects with *T. brucei*-specific staining (Anti-Invariable Surface Glycoprotein 65 [ISG65] and Anti-cross reacting determinant [CRD] and secondary polymer amplification
  - Automatised acquisition and double *in silico* blind reading, pictures annotation and archiving
- 3- Preliminary tests for the detection of trypanosomes by Raman spectroscopy:
  - For each subject at each time point, one DBS from the field and one FFPE slide generated for IHC at IP Paris will be scanned by Raman spectroscopy at the University of Glasgow in the context of an exploratory procedure based on the measurements of biophysical parameters associated to the presence of trypanosomes.

• The results will not be uploaded in the central data base as the final analyses will rely on machine learning approaches after the end of the study.

## 8.5. Adverse event definitions and reporting

## 8.5.1. Adverse event definition

An AE will be defined as "any untoward medical occurrence in a patient or clinical trial subject administered a medicinal product and which does not necessarily have a causal relationship with this treatment. An AE can therefore be any unfavourable and unintended sign (including an abnormal laboratory finding, for example), symptom, or disease temporally associated with the use of a medicinal product, whether or not considered related to the medicinal product." (17).

Definition of an AE includes worsening (in severity and frequency) of pre-existing conditions ("Medical history") before first study treatment administration and abnormalities of procedures (i.e. ECG, X-ray, ophthalmologic or neurological examination etc.) or laboratory results which are assessed as "clinically significant".

## What is not an AE

- Medical conditions present at the initial study visit that do not worsen in severity or frequency during the study are NOT considered as AEs.
- Symptom exacerbation or worsening of the studied disease will NOT be considered as AEs nor captured on the AE page of the CRF if consistent with the anticipated natural progression of the disease (overall and for this given subject).
- Lack of efficacy of the IP is not considered as an AE.

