## 2. Study objectives and endpoints

## 2.1. Objectives

## 2.1.1. Primary objective

To assess the safety and tolerability of a single dose of acoziborole compared with placebo during a follow-up period of 4 months in seropositive individuals who are not confirmed parasitologically.

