## 3. Study design and study design rationale

#### 3.1. Study design

This is a randomised, multicentre, double-blind, placebo-controlled, parallel-arm phase II/III study to assess the safety and tolerability of a single dose of acoziborole compared with placebo in adolescent and adult subjects seropositive to human African trypanosomiasis due to *T.b. gambiense* (g-HAT positive; not confirmed parasitologically [no demonstration of the parasite in any body fluid via microscopy]) in DRC and Guinea.

The double-blind, placebo-controlled nature of the study design will aid with minimising bias with the parallel-arm design allowing between subject comparison.

Subjects will be hospitalised at least 1 day before study treatment commences and will be randomised in a 3:1 ratio to acoziborole or matched placebo on Day 1 of the study. Following hospitalisation, subjects will attend follow-up visits at the study centre at 1- and 4-months post-treatment. At months 2 and 3, investigator contacts will be established between the site and subjects to ensure close follow-up of subjects and encourage study adherence. An on-site unscheduled visit will be proposed if deemed necessary by the investigator. Any subject with a positive parasitological test result during the study will end their participation in the study and be referred to the NSSCP for appropriate standard treatment.

In addition, a sub-study 'TrypSkin' to assess the presence of extravascular dermal *T.b. gambiense* in this population, will be proposed to subjects having given their consent to participate in the seropositive safety main study (in clinical sites participating in the sub-study only). Subjects can decide whether to participate or not in the sub-study independently of his/her participation in the main safety study.

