## 4.2. Exclusion criteria

The presence of any of the following criteria will exclude a subject from study enrolment:

- Individuals parasitologically confirmed in blood and/or lymph
- Previously treated for g-HAT
- Severe malnutrition, defined as body mass index (BMI) <16 kg/m^2
- Pregnant or breast-feeding women
- For women of childbearing potential:
  - Urine pregnancy test positive
  - Do not accept contraceptive protection (i.e. condom or sexual abstinence) from enrolment up to 3 months after dosing
- Clinically significant medical condition and/or abnormal laboratory results that could, in the opinion of the Investigator, jeopardise the subject's safety or participation in the study

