## 8.5.4. Eliciting adverse event information

The investigator is required to report all directly observed AEs and all AEs spontaneously reported by the trial subject using concise medical terminology. In addition, to avoid bias in eliciting AEs, each trial subject will be questioned about the occurrence of AEs during hospitalisation period and study follow-up visits, with general, non-leading questions such as *"Since xxx (e.g. last visit) have you had any health problem?"* or *"How are you feeling?"* 

All AEs (serious and non-serious) must be recorded on the source documents and CRFs regardless of the assumption of a causal relationship with the study drug(s). The definition, reporting period, and reporting requirements for AEs are described respectively in sections 8.5.1, 8.5.5 and 8.5.8).

Information on AEs must be evaluated by a physician.

Each AE is to be classified by the investigator as serious or non-serious (see definition of a SAE in section 8.5.3). This classification will determine the reporting procedure for the event.

In addition, the frequency, seriousness (see section 8.5.3), severity (see section 8.5.6), and causality (see section 8.5.7) assessment of AEs will be described.

Non-serious AEs are to be reported in the CRF, including description of the event, onset date, duration, severity, seriousness, relationship to all study drugs, actions taken and outcome.

In the CRF, a given AE will be recorded only once per subject, and the severity recorded will be the maximum level reached. If several distinct episodes of the same condition occur, their number will be recorded in the CRF.

SAEs will be reported both on the AE page of the CRF and the SAE forms.

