The AE can occur in both periods for the same subject (i.e. the event is still present at the second time period). However, for the period analysis the AE start date will be used to identify AEs in each period. The denominator of occurrence rate in each period will respectively be the number of subjects who receive at least one tablet of study treatment during the first time period and the number of subjects attending the 4-month visit or have reported a TEAE during the second time period. All statistics will be provided per time period to separately assess and interpret early events probably attributed to study treatment and late events that could be attributed to the disease or are persistent.

The time course of treatment effect will be analysed using the log rank test stratified by study centre and will be performed on the time to occurrence of TEAEs, taking into account the attrition rate of subjects who are being followed up. A loss to follow-up or a withdrawal will be censored at the time of the last attended visit. The Kaplan-Meier estimates of the proportion of subjects without any TEAE in each treatment group will be presented graphically to assess the time course of the response.

The hierarchy of testing reflects the sequence of testing from the more general effect to the most specific effect. There is a multiplicity of testing issue and an inflation of type I error that cannot be discarded. However, no adjustments of type I error are planned for this study as this study has been designed to detect any potential safety issues rather than confirming and investigating a safety concern.

The rate of occurrence of AEs will be analysed by the true positive status (subjects with parasites detected during the follow up period) in either treatment or placebo groups.

The rate of conversion to parasite positive and the rate of return to seronegative over 4 months will be analysed descriptively using frequency and proportion by treatment group.

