#### Analysis of secondary clinical and diagnostic parameters

Dermal trypanosomes may be the cause of dermatitis and/or pruritus, therefore a secondary clinical and exploratory question of interest is:

Does acoziborole reduce the occurrence at 4 months of dermatitis and/or pruritus signs or symptoms in comparison with placebo?

The secondary clinical parameter will be the occurrence/presence of dermatitis and/or pruritus signs or symptoms at 4 months.

The same approach as for the primary diagnostic parameter will be used for the occurrence of dermatitis or pruritus.

Current specific molecular diagnostic methods are known to be of low sensitivity. The TrypSkin sub-study aims at testing new methods to overcome this weakness.

Secondary diagnostic parameters will be the occurrence of IHC+ results in skin, TBR-PCR+ and/or 18S-PCR+ in blood and/or skin, as well as novel diagnostic parameters corresponding to occurrence of positive results by qPCRs, multiplex RT-qPCRs and SHERLOCK in blood and/or skin.

The secondary analyses will be exactly the same as the primary diagnostic parameters.

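### The AE definition leaves out worsening of the studied disease in subjects without confirmed disease, so part of the any-TEAE endpoint rests on a judgement the plan gives no means to make

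*Protocol*

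**What the plan says.** - **The exclusion.** Protocol 8.5.1, under What is not an AE: "Symptom exacerbation or worsening of the studied disease will NOT be considered as AEs nor captured on the AE page of the CRF", with the condition "if consistent with the anticipated natural progression of the disease (overall and for this given subject".
- **The population.** The primary objective (Protocol 2.1.1) concerns safety "in seropositive individuals who are not confirmed parasitologically". Protocol 4.2 excludes "Individuals parasitologically confirmed in blood and/or lymph". Protocol 3.1 adds: "Any subject with a positive parasitological test result during the study will end their participation in the study".
- **The general recording rule.** Under Protocol 8.5.4, all AEs "must be recorded on the source documents and CRFs regardless of the assumption of a causal relationship". The main definition in 8.5.1 counts worsening of a pre-existing condition as an AE.
- **The endpoint.** Protocol 10.7.1 makes the primary endpoint binary: any TEAE or none. SAP 3.2 includes events that began before dosing and worsened afterwards, and makes no exception for the disease.
- **The planned interpretation.** Protocol 10.7.1 splits TEAEs into an in-hospital period and a later period, and wants to interpret separately "late events that could be attributed to the disease or are persistent". Protocol 10.7.1 and SAP 5.1 also plan AE rates by true positive status, meaning parasites detected during follow-up.
- **Symptoms linked to the parasite.** Protocol 10.8: "Dermal trypanosomes may be the cause of dermatitis and/or pruritus".

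**The concern.** An investigator applying this bullet must decide whether a symptom is the expected course of HAT in a person in whom HAT has not been shown. If the answer is yes, the symptom does not reach the AE page and so cannot count as a TEAE. Two investigators could treat the same itch or rash differently, one recording it and the other leaving it out as disease.

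The trial exists to find safety signals, and its primary endpoint is meant to be independent of cause. Disease attribution already has a place in the protocol: 8.5.7 lists worsening of an existing condition among the matters to weigh when judging causality. The bullet in 8.5.1 moves that judgement forward, from how an event is classified to whether it is recorded. Protocol 8.5.3 defines a serious event as a kind of AE, so an event ruled not to be an AE could also escape classification as serious.

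**Working it through.** **1. Can the condition be applied?** It requires an anticipated natural progression, both in general and for the individual. Confirmed cases are excluded at entry, and anyone confirmed later leaves the study. The clause therefore acts almost entirely on subjects without established disease. Neither document sets out an expected course or a symptom list for them.

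**2. The rules side by side.**

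| Place | What happens to a symptom that worsens after dosing and might be HAT |
|---|---|
| Protocol 8.5.1, main definition | AE, if a pre-existing condition worsened |
| Protocol 8.5.1, What is not an AE | Not on the AE page, if judged natural progression |
| Protocol 8.5.4 | All AEs recorded, whatever the assumed cause |
| SAP 3.2 | TEAE, with no disease exception |
| Protocol 10.7.1 | Late TEAEs possibly due to disease are to be interpreted; AEs analysed by true positive status |

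The second row can remove the events that the last row needs.

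**3. What is captured elsewhere?** Clinical examination, including HAT signs and symptoms, takes place at screening, D5, M1 and M4, and dermatological examination at screening, M1 and M4 (Protocol Table 1). SAP 5.2.8 compares presence or absence of signs and symptoms between arms. Dermatitis and/or pruritus at month 4 is a sub-study endpoint (Protocol 10.8, SAP 5.3.1). None of these feeds the TEAE endpoint. Between dosing and D5 no clinical examination is scheduled. AEs are asked about daily, but the bullet governs what then counts as one. Protocol 3.3 reports that 97.7% of related TEAEs in the pivotal study occurred within 5 days of dosing.

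**4. The plan's detection figures, reproduced.** Formula: 1 − (1 − p)^900, for 900 subjects on acoziborole.
- p = 1%: 99.99% (Protocol Table 5 gives 99.9%)
- p = 0.5%: 98.90% (Protocol 10.1.1 gives 98%)
- p = 0.2%: 83.50% (Protocol 10.1.1 gives 83.5%)
- p = 0.1%: 59.36% (Protocol Table 5 gives 59.36%)

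These assume that every event is recorded.

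**5. Sensitivity to omission.** Let c be the share of affected subjects whose event is recorded. The documents give no value, so c is an assumption. It is relevant only to symptoms that could be read as HAT. Detection becomes 1 − (1 − c·p)^900.

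| True incidence | c = 1 | c = 0.9 | c = 0.75 | c = 0.5 |
|---|---|---|---|---|
| 0.5% | 98.9% | 98.3% | 96.6% | 89.5% |
| 0.2% | 83.5% | 80.2% | 74.1% | 59.4% |
| 0.1% | 59.4% | 55.5% | 49.1% | 36.2% |

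**6. Effect on the excess rate.** The planning case in Protocol 10.1.2 is 2% on acoziborole and 1% on placebo. The observed excess rate is c_A × 2% − c_P × 1%.
- Equal omission, c = 0.9 / 0.75 / 0.5: excess rate 0.90% / 0.75% / 0.50% instead of 1.00%. NNT = 1/ER goes from 100 to 111 / 133 / 200.
- Omission on placebo only, c_P = 0.75: 2.00% − 0.75% = 1.25%.
- Omission on acoziborole only, c_A = 0.75: 1.50% − 1.00% = 0.50%.

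Equal omission shrinks the difference. Unequal omission can move it either way. For the composite any-TEAE endpoint, an omitted event changes a subject's status only if that subject has no other recorded TEAE.

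**The case against.** The strongest reply is that the clause limits itself. If there is no confirmed disease, natural progression for this subject normally cannot be asserted, so the default applies and the event is recorded. Exacerbation or worsening also does not obviously cover a new symptom, and disease progression is a poor explanation for something that appears in the first five days in hospital. This stands as the sensible reading of the clause. But the protocol does not state it, and sites are left to find it for themselves.

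Second, judgement is blinded. If acoziborole clears infection, disease worsening would concentrate on placebo. Leaving it out would then raise the excess rate for acoziborole, which is conservative, while recording it could mask harm. This is a fair point against assuming any direction of bias. It is met by recording the events with their attribution and analysing with and without them.

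Four stronger readings are tempting but not supported:
- That the exclusion is blanket. It carries a condition.
- That the analysis section expects drug reactions among the excluded events. Protocol 10.7.1 treats early events as probably due to treatment and late ones as possibly due to the disease; what may go missing is disease-attributable TEAEs.
- That the events vanish from the database. They leave the AE page, and some remain in the examination and sub-study data.
- That headache shows drug reactions being lost. Protocol 1.4 lists headache among the frequent AEs in the healthy-volunteer study, but reports similar AE frequency and severity on active and placebo.

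Nor does the hypothesised upper limit of 20–25% dermal carriage (Protocol 10.1.1) size the problem. It concerns parasites in skin among RDT-positive sub-study subjects, not symptomatic HAT.

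**Conclusion.** The point holds as a problem of ascertainment and internal consistency. The bullet makes recording for the primary endpoint depend on a judgement that the documents give no basis for in this population. It is in tension with Protocol 8.5.4, SAP 3.2 and Protocol 10.7.1. The other sources of symptom data do not close the gap, because they do not feed the TEAE endpoint and include no clinical examination between dosing and D5.

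The size is unknown. The figures for incomplete recording rest on assumed values of c. They show only that a modest loss (c = 0.9) takes detection of a 0.2% event from 83.5% to 80.2%, and that a loss of half takes it to 59.4%. Omission that is equal across blinded arms biases the excess rate toward no difference, which is the undesirable direction in a safety trial. A reader might infer that the clause favours acoziborole; the documents do not establish any difference by arm, nor its direction. The change is worth making because it is cheap and bears on the primary endpoint, not because a large loss has been shown.

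**What to change.** 1. **Protocol 8.5.1.** Delete the bullet, or state that it does not apply to parasitologically unconfirmed subjects. New or worsened signs and symptoms are then recorded as AEs, with suspected HAT noted as the attribution.
2. **Reconcile** the main AE definition and the bullet in 8.5.1 with 8.5.4 and 10.7.1, so that one rule decides what is recorded.
3. **SAP 5.1.** Report the TEAE excess rate with and without HAT-attributed events.
4. **Subjects already followed under the current wording.** Before unblinding, list any new or worsened finding at the clinical or dermatological examinations that has no matching AE. This will not recover symptoms that came and went between examinations, and the report should say so.

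**Cost.** A wording change, a reminder to sites, a place to note the attribution, somewhat more AE entries, and one extra listing and analysis. Protocol version 3.0 already looks back on about 1.5 years of conduct (9.2), so the recording rule would change partway through the trial. The date of the change should be reported.
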